8.4.2 End of study

The randomisation code will be broken by the study statistician once data entry has been completed, the database locked, and the per-protocol population for analysis established and the Statistical Analysis Plan (SAP) finalised and approved. The Sponsor will provide written permission to the study statistician prior to the breaking of the randomisation code.

8.5 Formulation

8.5.1 Investigational medicinal products

DEN-181 is a sterile suspension of egg phosphatidylcholine (EPC) and egg phosphatidylglycerol (EPG) liposomes (approx. 100 nm diameter, lipid molar ratio 90:10) containing collagen II peptide (Pro273Hyp collagen₂₅₉₋₂₇₃) and calcitriol formulated in sucrose-buffered histidine buffer. Product is filled in 2 mL amber glass vials for single use. Each vial contains 1.0 mL extractable volume of DEN-181 containing 0.6 µg/mL calcitriol and 45µg/mL collagen II peptide. DEN-181 was manufactured by Evonik Canada Inc, (Burnaby, British Columbia, Canada) according to cGMP.

The placebo is sterile saline for injection (0.9%NaCl).

DEN-181**Dendright Pty Ltd**

Product specifications and the associated manufacturing process are provided in the IB and a summary is provided below:

Table 8-1 Summary of DEN-181

Name:	DEN-181
Characteristics & Physical State:	Suspension of egg phosphatidylcholine (EPC): and egg phosphatidylglycerol (EPG) liposomes (approx. 100 nm diameter, lipid molar ratio 90:10) containing 0.6 µg/mL calcitriol and 45µg/mL collagen II peptide. The material will be provided frozen.
Supplied by:	Evonik Canada Inc. (Burnaby, British Columbia, Canada)
Storage Conditions:	Store at minus 20 degrees Celsius +/- 5 degrees
Package	2 mL amber vial

8.5.2 Supply, packaging and labelling, storage and handling

The batch number, expiry date and documented compliance with product release specification criteria will be included in the DEN-181 Certificate of Analysis. Evidence of cGMP will also be made available. The IMP will be supplied to the study site after receipt of required documents in accordance with the Sponsor authorised release procedures. Clinical trial labels will comply with Annex 13 of the Australian Code of Good Manufacturing Practice for Medicinal Products – Manufacture of Investigational Medicinal Products.

The following information will appear as secondary labelling i.e., on the label of the outermost container of the study investigational product vials:

- Dendright Pty Ltd, St. Lucia, QLD, Australia
- Protocol number: DEN-17-01-RA
- DEN-181 containing 0.6 µg/mL calcitriol and 45µg/mL collagen peptide
- Lot number
- Investigator Name
- Sterile aqueous suspension for subcutaneous injection
- Fill volume: 1.1 ml
- For Clinical Trial Use Only
- Store at: -20°C (±5°C)
- Date of manufacture
- Retest date.

The following information will appear as primary labelling i.e., on the label of the study investigational product vials:

- Dendright Pty Ltd.
- Protocol number: DEN-17-01-RA
- DEN-181 containing 0.6 µg/mL calcitriol and 45µg/mL collagen peptide
- Lot number
- Retest Date
- Fill volume: 1.1 ml

DEN-181

Dendright Pty Ltd

- Participant identification number
- Sterile aqueous suspension for subcutaneous injection.
- Store at: -20°C (±5°C)
- For Clinical Trial Use Only.

The packaging lot numbers will be recorded on the investigational product accountability record.

DEN-181 must be stored in a secure area with access limited to the pharmacist or responsible party and authorized staff. The vials and outer packaging will be stored frozen at -20 +/-5 °C, and thawed to room temperature (RT) prior to use. DEN-181 should be used within 4-6 hours of equilibration to RT. The DEN-181 vials contain 0.6 µg calcitriol and 45µg collagen peptide per 1.0 mL.

The Investigational Product must be prepared under aseptic conditions. Further details regarding preparation and administration of IMP are supplied in the Pharmacy Manual. The clinical study personnel must maintain a temperature log for the freezer which houses the investigational product. Daily minimum and maximum temperatures will be recorded in the temperature logs.

8.5.3 Dosage and administration of test drugs

For both Parts A and B, the different dosage volumes of IMP will be administered in the following way:

- Subjects will receive 100µl subcutaneous injections approximately 10 cm above the elbow joint overlying the deltoid muscle of the left upper arm. Where possible the same arm will be injected throughout the course of the study.
- For 300µl subcutaneous injections, 150µl will be delivered 10 cm above the elbow joint overlying the deltoid muscle of each upper arm.
- For 1000µl subcutaneous injections, 250µl will be delivered 10 cm above the elbow joint overlying the deltoid muscle of each upper arm and approximately 5 cm from the groin on each upper thigh.

The injection site will be cleaned prior to administration of the IMP by cleaning with an alcohol swab and air dried.

The participant must remain under supervision at the trial site for at least 4 hours after administration of the IMP. Vital signs including heart rate, supine pulse rate, temperature and supine blood pressure (SBP and DBP) and local reaction at the injection site will be assessed following IMP administration.

8.5.4 Dispensing and accountability

DEN-181 is supplied for use only in this clinical study and should not be used for any other purpose. The Investigator's nominee will prepare the investigational product according to the procedure set out in the Pharmacy Manual.

The Investigator will be responsible for maintaining accurate records for all study medications dispensed and returned. The inventory must be available for inspection by the study monitor. Study product supplies, including partially used or empty (describe unit/container e.g. syringe, tablets, vials, bottle, pack) and the dispensing logs, must be accounted for by the study monitor and returned to the drug repository for destruction at the end of the study.

DEN-181

Dendright Pty Ltd

When requested in writing by the Sponsor, unused study medication supplies may be destroyed by the Investigator provided such disposition can be performed safely. Records shall be maintained by the Investigator or any such alternate disposition of the study medication. These records must show the identification and quantity of each unit disposed of, the method of destruction (taking into account the requirements of local law), and the person who disposed of the test substance. Such records shall be submitted to the sponsor.

9 CONCURRENT MEDICATIONS AND TREATMENTS

At each study visit, the Investigator should question the subject about any medication taken including vitamin supplements and herbal remedies. Any concurrent medications will be recorded in the subject's records and the CRF. Any changes in doses or introduction of a new medication during the course of the study will also be recorded.

9.1 Special dietary requirements

There are no special dietary requirements.

9.2 Concurrent medications/treatments not permitted

9.2.1 Prior to study entry

Refer to exclusion criteria in Section 6.3 with particular note to the following medications and treatments that are not permitted:

- Currently receiving >10mg prednisone/day;
- Receipt of any live attenuated vaccines within 4 weeks prior to entry;
- Treatment with cytotoxic or immunomodulatory therapies such as radiotherapy, cyclophosphamide, mycophenolate, tacrolimus, PUVA, acitretin, cyclosporine or azathioprine;
- Concurrent treatment or treatment within 2 weeks of trial commencement with any DMARD other than MTX;
- Other investigational drugs.

9.2.2 During the study dosing period

Throughout the study medication dosing period, subjects may not receive any of the following concomitant medications:

- Immunomodulating agents (including immunosuppressive agents, interferon or other immune or cytokine-based therapies), and/or systemic chemotherapeutics;
- Chronic treatment with immune-suppressive therapy (stable use of asthma inhalers and topical corticosteroids are permitted);
- Subjects also should not receive any other vaccines during their participation in this study;
- Other investigational drugs.

NSAID and steroid therapy (e.g. intra-articular joint injection or daily oral prednisone at > 10 mgs/day) may be utilised, if required, after Day 29 of the study. Subjects can receive prednisone at < 10 mgs/day either stably or intermittently during the study.

All concurrent medications, including vitamin supplements and herbal remedies, must be recorded in the appropriate section of the CRF.

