
Study procedures:
	
Please refer to Table 1
 
This is a randomised, double blind, placebo-controlled, single centre, single-dose escalation and multiple dose, dose-ranging parallel group study to be performed in 2 parts.
 
Part A: Randomised double blind, placebo-controlled, single centre, single-dose escalation study at three dose levels; Part B: Randomised double blind, placebo-controlled single centre multiple dose, dose- ranging parallel group study at two dose levels.
 
The 2 dose levels to be tested in the 2 groups of Part B will be based upon review of the data in respect of safety and immunomodulatory assessments of the three dose levels tested in Part A by a Safety Monitoring Committee (SMC).
 
Screening Potential participants will be required to provide written informed consent prior to any study-specific screening procedures being performed.
 
Study Period Eligible subjects will return at Baseline (Day 1) to be randomised to receive the first treatment
 
Part A Up to 18 eligible participants will be randomised into Part A of the study. Three dose levels will be assessed in a single dose escalation study design. Participants will be assigned to a dose level. Dose Level 1 (4 active, 2 placebo), Dose Level 2 (4 Active, 2 placebo), Dose Level 3 (4 active, 2 placebo). At each dose level two sentinel subjects (1 active, 1 placebo) will be initially randomised. The remainder of the participants will be dosed no earlier than 7 days after dosing the sentinel group. Safety and tolerability at each dose level will be assessed by a Safety Monitoring Committee 14 days after the dose given to the final cohort participant before proceeding to a progressively higher dose level.
 
Part B Up to 40 eligible participants (30 active, 10 placebo) will be randomised into Part B of the study. The dose levels will be determined based on the results of Part A. Eligible subjects will be administered investigational medicinal product (IMP) on Days 1, 8 and 15 in Part B.
 
Vital signs will be recorded prior to all Investigational Medical Product administrations and at 15 minute intervals for 30 minutes following each dose. Vital signs will include supine blood pressure (systolic blood pressure (SBP) and diastolic blood pressure (DBP), heart rate, respiratory rate, and oral temperature. Subjects will be required to remain in the clinic for at least 4 hours after all Investigational Product administrations. Blood will be drawn for limited PK analysis pre-dose and at 1, 2 and 4 hours post administration of IMP in both parts A and B.
 
Participants will be encouraged to visit the study site on the same day every week (± 2 days) to ensure the lengths of the weeks are similar. Physical examinations, adverse events, vital signs, clinical laboratory parameters (haematology, chemistry, urinalysis) and concurrent medications will be recorded throughout the study. Serum pregnancy testing will be conducted for female participants at Screening and urine pregnancy tests before administration of each dose of IMP. If urine pregnancy testing is positive, a serum pregnancy test will be conducted and the IMP will not be administered until the result is available. If the serum pregnancy test is negative, administration of IMP will continue.

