7.2 Visit windows

Every effort should be made to keep to the study schedule.

Study Period	Acceptable Window
Screening	± 3 days
On-study (dosing)	± 2 days
Follow-up	± 7 days

The Sponsor or designee must approve all visits outside of these windows.

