7.3.3.2 Visit 4 (Day 15)

The subject will return to the clinic fourteen days following the first administration of the IMP for visit 4. The following procedures will be performed:

- Symptom directed physical examination (See Section 7.4.1)

- Vital Signs (See Section 7.4.1)
- DAS28CRPv4 Evaluation (see Section 7.4.7)
- For Subjects in Part B, review of Injection Site Reaction Diary (See Section 7.4.5)
- Blood samples for:
 - Haematology including ESR (See Section 7.4.3.)
 - Clinical chemistry including CRP (See Section 7.4.3)
- Blood Samples for Pharmacokinetic (Calcitriol) assessment (Part B only, See Section 7.4.3)
- Urine samples for urinalysis (See Section 7.4.3)
- Adverse event and concurrent medication questioning (see Sections 9 and 10)
- Urine sample for pregnancy testing (Part B only)

For subjects undergoing Part B of the study, once the above assessments have been performed the IMP will be administered:

- Subjects will be observed and vital signs will be measured at 15 and 30 minutes following the administration of IMP
- Subjects will remain in the clinic for at least four hours post-administration of IMP
- Blood samples for calcitriol concentration assessment will be taken 1, 2 and 4 hours after IMP administration
- The subject will be issued with an Injection Site Reaction Diary and instructed to view their injection site (s) at the same time each day and record their findings every day for 3 days (See Section 7.4.5).

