7.3.3.3 Visit 5 (Day 29)

The subject will return to the clinic 21 days following the first administration of the IMP for visit 5. The following procedures will be performed:

- Symptom directed physical examination (See Section 7.4.1)
- Vital Signs (See Section 7.4.1)
- DAS28CRPv4 Evaluation (see Section 7.4.7)
- For Subjects in Part B, review of Injection Site Reaction Diary (See Section 7.4.5)
- Blood samples for:
 - Haematology including ESR (See Section 7.4.3.)
 - Clinical chemistry including CRP (See Section 7.4.3)
- Blood Samples for Immunological Assessment including (See Sections 7.4.3 and 7.4.4):
 - Tetramer analysis
 - Anti-CCP2 titre (See Section 7.4.3)
 - Exploratory immune assays
- Urine samples for urinalysis (See Section 7.4.3)
- Adverse event and concurrent medication questioning (see sections 9 and 10)

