7.3.4 Visit 6 (Day 57) exit evaluation

The end of study visit (Visit 6) will be conducted in the clinic 56 days following the first administration of IMP. The following tests will be performed and documented as indicated on the CRF:

- Symptom directed physical examination (See Section 7.4.1)
- Vital Signs (See Section 7.4.1)
- DAS28CRPv4 Evaluation
- Blood samples for:
 - Haematology including ESR (See Section 7.4.3)
 - Clinical chemistry including CRP(See Section7.4.3)
- Urine samples for urinalysis and pregnancy testing (See Section7.4.3)
- An oral swab will be taken (See Section 7.4.8)
- Blood Samples for Immunological Assessment including (see Sections 7.4.3 and 7.4.4):
 - Anti-CCP2 (See Section 7.4.3)
- Adverse event and concurrent medication questioning (see sections 9 and 10)

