7.4 Details of scheduled assessments

7.4.1 Demographic data, medical history, physical examination, vital signs

Demographic data will include sex, race/ethnicity and date of birth.

The medical history will include any diagnosed medical conditions or surgical history.

A complete physical examination (including head, ears, nose, throat, lungs, lymph nodes, heart, abdomen and skin) at screening will be conducted to determine study eligibility. A modified physical examination will also be performed at Days 1, 8, 15, 29 and 57 and at the early termination visit if applicable. The symptom directed physical examinations will be performed based on signs and symptoms the subject has reported verbally and/or documented in the diary booklets. A symptom directed physical examination may also be performed if in the opinion of the Investigator if it is required.

Vital signs measured:

- Body temperature (degrees Celsius) aural
- Respiratory rate
- Pulse rate (sitting)
- Blood pressure (sitting)

Height and body weight will be measured and documented at the Screening visit.

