7.4.3 Blood and urine samples for laboratory tests

Blood and urine will be collected at all visits and should be within the visit window (see 7.2) Detailed instructions on the handling and processing of specimens are located in the Study Reference Manual. The following will be collected at the times specified in Section 7.3:

Haematology:	Haemoglobin, haematocrit, red blood cell (RBC) count , white blood cell and differential white blood cell count, platelet count, mean corpuscular volume (MCV), mean corpuscular haemoglobin concentration (MCHC), erythrocyte sedimentation rate (ESR).
Chemistry:	Sodium, potassium, chloride, bicarbonate, BUN, creatinine, total protein, albumin, serum amylase, phosphorus, AST, ALT, GGT, alkaline phosphatase, total bilirubin, glucose, CPK, calcium, uric acid, C-reactive protein (CRP)
Viral Serology:	HIV, HCV and HBV (at screening). HIV testing will be repeated after screening if there is a clinical suspicion that a subject may be at risk of infection.
Immunological:	HLA typing if required. HLA typing does not need to be repeated if part of medical record from an appropriately accredited laboratory, anti-CCP2 titre (if required), Rheumatoid Factor, Tetramer analysis (Collagen II peptide and other RA autoantigens), Exploratory immune assays (measures of humoral and T cell responses e.g. Interferon-gamma (IFN- γ) enzyme linked immunospot (ELIspot) assays, T-cell responses specific for RA autoantigens)
Urinalysis:	Protein, glucose, blood and microscopy (if abnormal).
Urine Pregnancy:	Human chorionic gonadotropin.
Serum pregnancy:	Human chorionic gonadotropin.
Pharmacokinetics:	Calcitriol concentration in plasma and pharmacokinetic indices

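### Section 7.3.3.3 dates Visit 5 seven days early (21 days after first dose is Day 22, not Day 29); the visit's window and, secondarily, the steroid release in 9.2.2 should be tied down with it

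*Protocol*

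**What the plan says.** **Visit date.** The heading of Protocol section 7.3.3.3 names Visit 5 as Day 29, and Table 1-1 has it in the D29 column. Section 7.4.1 agrees: "A modified physical examination will also be performed at Days 1, 8, 15, 29 and 57". The instruction under the 7.3.3.3 heading differs: "The subject will return to the clinic 21 days following the first administration of the IMP for visit 5". The neighbouring visits are worded the same way. For Visit 4: "The subject will return to the clinic fourteen days following the first administration of the IMP for visit 4". Visit 6 "will be conducted in the clinic 56 days following the first administration of IMP".

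**Visit window.** Section 7.2 gives ±2 days in the row that begins "On-study (dosing" and ±7 days in the Follow-up row. It does not assign visits to rows. The synopsis encourages attendance "on the same day every week (± 2 days"). Section 7.4.3 ties sampling to the window: "Blood and urine will be collected at all visits and should be within the visit window".

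**Drug release.** Section 9.2.2 says that NSAID and steroid therapy, with intra-articular injection and prednisone above 10 mg/day as its examples, "may be utilised, if required, after Day 29 of the study". Prednisone below 10 mg/day is allowed throughout.

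**What Visit 5 carries.** In Table 1-1, tetramer analysis and PBMC storage are scheduled on D1, D8 and D29 only.

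**The concern.** Visit 5 supplies the last tetramer and PBMC sample in both parts. In Part B it is the only one after doses 2 and 3, because the Day 8 blood is drawn before dose 2 (7.3.3.1) and none is taken for this purpose on Day 15. These data support a secondary endpoint, and under section 13.8 the Part A immunomodulation data help choose the Part B doses. An operative instruction that misdates this visit could therefore shift the dose-to-sample interval, or make it vary between patients if some are booked from the text and others from the table.

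The release rule in 9.2.2 bears on the same sample. It names a day, not completion of the Visit 5 procedures. A steroid beyond the permitted dose would normally be started for active disease, so any exposure before the sample would depend on disease activity, and a pre-treatment sample cannot be recovered afterwards.

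**Working it through.** **1. The protocol's day numbering.** First dose is on Day 1, so study day = 1 + days since first dose. Checked against each visit text:

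| Visit | Days after first dose (text) | Computed day | Day in heading and Table 1-1 |
|---|---|---|---|
| 3 (7.3.3.1) | 7 | 1 + 7 = 8 | 8 |
| 4 (7.3.3.2) | 14 | 1 + 14 = 15 | 15 |
| 5 (7.3.3.3) | 21 | 1 + 21 = **22** | **29** |
| 6 (7.3.4) | 56 | 1 + 56 = 57 | 57 |

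Three of four agree and only Visit 5 fails. Day 29 needs 29 − 1 = 28 days. The text is 29 − 22 = 7 days early.

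**2. Effect on the dose-to-sample interval if the text is followed.**
- Part B, last dose on Day 15: 22 − 15 = 7 days, against 29 − 15 = 14.
- Part A, single dose on Day 1: 22 − 1 = 21 days, against 29 − 1 = 28.

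**3. Would the visit window catch the error?**
- ±2 days: Days 27 to 31. Day 22 is 27 − 22 = 5 days too early, so it would be flagged.
- ±7 days: Days 22 to 36. Day 22 is exactly the lower limit, so it would pass.

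Which window applies is not stated. Favouring ±2 are the On-Study Period banner over D29 in Table 1-1, the title of section 7.3.3 and the synopsis target. Favouring ±7 are two facts: no dose is given at Visit 5, and the synopsis counts the time after the last dose as post-treatment follow-up (15 + 42 = Day 57 in Part B; 1 + 56 = Day 57 in Part A). The evidence leans to ±2 without ruling out ±7.

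**4. The release in 9.2.2, read as a calendar day.** Treatment is then allowed from Day 30. Full treatment days before the latest in-window Visit 5 = (29 + window) − 30.
- ±2: 31 − 30 = 1 day (Day 30).
- ±7: 36 − 30 = 6 days (Days 30 to 35).
- Visit 5 on or before Day 29: none.

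If Day 29 in 9.2.2 means Visit 5 itself, there is no gap under either window. The protocol gives no rate of late visits or of steroid starts, so the number of affected patients cannot be computed.

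**The case against.** On the date, it can fairly be said that this is a one-number slip. The section's own heading, Table 1-1 and 7.4.1 all give Day 29, and section 7.1 points to the table as the schedule. A site would have to follow one number against all three. This stands as a limit on likelihood. A reader might infer that Part B patients will in fact be sampled 7 days after dose 3, and the documents do not support that prediction. They show only that the sentence is wrong and that section 7.2 may not catch a visit booked from it.

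The objection to the drug-release point is stronger. The protocol often uses a day number as a visit label, as in 7.4.1 and in the reference to the Day 15 visit in 13.8, so release after Day 29 may well mean after Visit 5. A reader might infer that the protocol lets restricted steroid contaminate the last sample. That follows only from the calendar-day reading, and 9.2.2 does not say which reading is meant. Nor is 1 day a bound set by the protocol: it holds only under ±2, and 7.2 also allows visits outside the windows with sponsor approval.

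Other provisions soften the consequence. Concurrent medications are recorded, so exposed samples can be identified. A need for interfering medication is already a listed reason for withdrawal (12.2). Low-dose prednisone is allowed throughout, so steroid-free sampling was never the design. Section 13.1 makes the analyses descriptive. Handling of exposed samples may be set in the SAP, which is not at hand. All of this stands, and it makes the release rule an optional clarification and not an error.

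**Conclusion.** Section 7.3.3.3 is wrong as written: Visit 5 is placed 7 days early and should be 28 days after first dose. This rests only on the protocol's own day numbering, which its other visit texts confirm. The unassigned window in 7.2 is a related gap, because under ±7 a Day 22 visit would count as in window.

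The 9.2.2 point is secondary and conditional. On the calendar-day reading, possible pre-sample treatment spans 0 to 1 full day under ±2 and 0 to 6 under ±7. On the visit reading it is nil.

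The practical impact is probably small: the heading and schedule agree on Day 29, few patients are likely to be both late for Visit 5 and newly in need of restricted treatment, and the results concerned are secondary and descriptive. The case for acting is that the sample cannot be repeated and the corrections cost almost nothing.

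**What to change.** - **7.3.3.3:** change 21 days to 28 days.
- **7.2:** add a line stating that the ±2-day window applies to Visit 5.
- **9.2.2:** make the release conditional on the Visit 5 (Day 29) blood samples and DAS28CRPv4 having been obtained, in place of the bare day number. If treatment is needed sooner, bring Visit 5 forward within its window. Urgent treatment is never to be delayed for sampling.

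The cost is one number, one line and one phrase, plus a few rescheduled Visit 5 appointments. With the release tied to the samples, restricted treatment started under this rule would precede sampling by 0 days under either window, apart from urgent cases, which the medication record would identify.
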